## 1. PROTOCOL SYNOPSIS

**Name of Sponsor/Company:** Acceleron Pharma Inc., [name]

**Name of Investigational Product:** Dalantercept (also known as ACE-041)

**Name of Active Ingredient:**

Dalantercept is a recombinant fusion protein consisting of the extracellular domain (ECD) of human activin receptor-like kinase 1 (ALK1) linked to the Fc (hinge, CH2 and CH3 domains) portion of human immunoglobulin G1 (IgG1).

**Title of Study:**

A Phase 2 randomized, double-blind study of dalantercept plus axitinib compared to placebo plus axitinib in patients with Advanced Renal Cell Carcinoma

**Study Center(s):** Approximately 60 centers

**Phase of Development:** 2

**Objectives:**

**Part 1**

Primary:

- Evaluate safety and tolerability of dalantercept plus axitinib in patients with advanced renal cell carcinoma (RCC) to determine the recommended Phase 2 dose level of dalantercept plus axitinib for Part 2

Secondary:

- Evaluate progression free survival (PFS), overall survival (OS), objective response rate (ORR = complete response [CR] + partial response [PR]), duration of response (DR), and disease control rate (DCR includes CR, PR, or stable disease [SD])
- Evaluate the pharmacokinetic (PK) profiles of dalantercept and axitinib when used in combination
- Explore association of the expression of bone morphogenetic protein (BMP) 9/10, ALK1 and/or other relevant pharmacodynamic (PD) markers in archived tumor biopsy with tumor response and/or other assessments of clinical response
- Explore association of serum pharmacodynamic (PD) biomarkers with assessments of response

**Part 2**

Primary:

- To determine whether treatment with dalantercept plus axitinib prolongs progression free survival (PFS) compared to placebo plus axitinib in patients with advanced RCC

Secondary:

- Determine the PFS for the subgroups of patients who had 2 or more prior lines of

anticancer therapy receiving dalantercept plus axitinib vs. placebo plus axitinib

- Evaluate safety and tolerability of dalantercept plus axitinib
- Evaluate overall survival (OS), objective response rate (ORR), duration of response (DR), and disease control rate (DCR)
- Explore association of the expression of BMP9/10, ALK1 and/or other relevant pharmacodynamic (PD) biomarkers in archived tumor biopsy with tumor response and/or other assessments of clinical response
- Explore association of serum pharmacodynamic (PD) biomarkers with assessments of response

**Methodology:**

This is a two-part, multi-center, randomized, double-blind, placebo-controlled Phase 2 study to evaluate the safety, tolerability, efficacy, PK and PD of dalantercept plus axitinib in patients with advanced RCC.

**Part 1 (dose escalation):**

Patients who have signed the informed consent form (ICF) and meet the eligibility criteria will be enrolled in Part 1 of the study. Part 1 will include up to four cohorts (planned dalantercept dose levels: 0.6, 0.9, 1.2 and 1.5 mg/kg) of a minimum of 3 patients each to determine the maximum tolerated dose (MTD) level of dalantercept plus standard dosing of axitinib. Patients will receive dalantercept once every 3 weeks by subcutaneous (SC) injection and continuous dosing of axitinib at a starting dose of 5 mg orally (PO) twice daily (BID), with dose modification of each drug as indicated per protocol or prescribing information, respectively. Treatment will be discontinued for progression of disease, as defined by RECIST (version 1.1, [Appendix 1](#)).

At least three patients must complete the Day 29 visit at each dalantercept dose level with full review of data through Day 29 by the Safety Review Team (SRT) prior to escalation to the next higher dose level. The SRT may recommend adding an additional three patients to the current dose level for further evaluation prior to treatment of the next cohort with the planned (higher) dose level, escalating to an intermediate dose level or discontinuing escalation.

**Expansion cohort:**

Once the MTD or maximum tested dose level has been determined by the SRT and Sponsor, up to a total of 20 patients may be enrolled at up to 2 different dose levels at or below the MTD to further evaluate safety, tolerability, and preliminary anti-tumor activity of dalantercept plus axitinib and to determine the recommended Phase 2 dose level for Part 2. The SRT will meet after a minimum of 10 patients have been evaluated for a minimum of 29 days to review safety data and vital signs data to assess safety. Treatment will be discontinued for progression of disease, as defined by RECIST (version 1.1, [Appendix 1](#)).

The initiation of Part 2 will be based on evaluation of cumulative safety and clinical activity of dalantercept plus axitinib in Part 1.

**Part 2 (randomized, double-blind, placebo-controlled):**

Based upon recommendations from the SRT and per sponsor decision, 130 patients will be enrolled and randomized in a 1:1 configuration to receive either the recommended Phase 2 dose level for Part 2 of dalantercept as identified in Part 1, (n=65) or placebo (n=65) plus axitinib. The randomization will be stratified by prior mammalian target of rapamycin (mTOR) inhibitor

therapy and prior immune therapy. Patients will receive dalantercept/placebo once every 3 weeks by SC injection and continuous dosing of axitinib at a starting dose of 5 mg PO BID, with dose modification of each drug as indicated per protocol or prescribing information, respectively. Treatment will be discontinued for progression of disease, as defined by RECIST (version 1.1, [Appendix 1](#)) or discontinuation of either dalantercept/placebo or axitinib.

All patients will undergo a final visit approximately 1 month following their last dose of dalantercept or placebo, and begin follow-up for progression of disease and patient survival. If a patient has a positive anti-drug antibody (ADA) result at the last visit, the patient may be asked to return for additional ADA testing every three months, until a negative result is obtained or the result is considered to be stabilized.

**Number of Patients (planned):**

Up to 44 patients will be enrolled in the dose escalation phase of the study (Part 1) and approximately 130 patients will be enrolled in the randomized phase of the study (Part 2) for a total of up to approximately 174 patients. Patients who are not evaluable may be replaced in Part 1 only.

**Duration of Treatment:**

The total duration of participation in the study will vary for each patient. There will be a 14 day screening period, a treatment period lasting for as long as patients are eligible to remain on-study, a final visit approximately 1 month after the last dose of dalantercept or placebo, and follow-up for progression of disease and patient survival. If a patient has a positive ADA result at the last visit, the patient may be asked to return for additional ADA testing every three months, until a negative result is obtained or the result is considered to be stabilized.

**Diagnosis and Main Criteria for Eligibility**

**Inclusion Criteria:**

1. Age  $\geq$  18 years.
2. Histologically confirmed, advanced, predominantly clear cell renal cell carcinoma (RCC).
3. **Part 1:** Progression of disease following up to three lines of prior therapy, including at least one approved VEGF receptor tyrosine kinase inhibitor (TKI) for RCC. Adjuvant therapy is permitted as one line of prior therapy.

**Part 2:** Progression of disease following one VEGF pathway inhibitor for RCC (sunitinib, pazopanib, sorafenib, bevacizumab, tivozanib, or cabozantinib) inclusive of adjuvant therapy if there was documented disease progression during treatment. Patients may have received one additional line of an approved mTOR kinase inhibitor (everolimus, temsirolimus) Prior exposure to investigational and/or approved anticancer immune therapies is permitted.

4. A minimum of 1 week since the last dose of prior therapy (a minimum of 4 weeks since anticancer immune therapy or bevacizumab +/- interferon).
5. Measurable disease that is evaluable by Response Evaluation Criteria in Solid Tumors (RECIST) v1.1 ([Appendix 1](#)).
6. Eastern Cooperative Oncology Group (ECOG) performance status of

0 or 1 ([Appendix 2](#)).

7. Life expectancy of at least 12 weeks.
8. Clinical laboratory values that meet the following criteria within 72 hours prior to study day 1:
  - Hematology (in the absence of hematopoietic growth factor support):
    - Absolute neutrophil count (ANC)  $\geq 1,500$  / $\mu$ L ( $\geq 1.5 \times 10^9$  /L).
    - Hemoglobin  $\geq 9$  g/dL ( $\geq 90$  g/L).
    - Platelet count  $\geq 100,000$  / $\mu$ L ( $\geq 100 \times 10^9$  /L).
  - Measured or calculated creatinine clearance, using the Cockcroft-Gault formula, ([Appendix 5](#))  $\geq 40$  mL/min.
  - Total bilirubin  $\leq 1.2$  x upper limit of normal (ULN). Patients with confirmed Gilbert's Syndrome may have bilirubin levels up to 3.0 mg/dL.
  - Aspartate aminotransferase (AST) and alanine aminotransferase (ALT)  $\leq 2.5$  x ULN ( $\leq 5$  x ULN if liver metastases are present).
  - Serum albumin  $\geq 3.0$  g/dL ( $\geq 30$  g/L).
  - Sodium  $\geq 133$  mEq/L ( $\geq 133$  mmol/L).
  - Urinary protein  $< 2+$  by urine dipstick or urinalysis. If  $\geq 2+$ , then patient may be enrolled if 24-hour urine protein  $< 2$  g/24hr.
9. Females of child bearing potential (defined as sexually mature women who have not undergone hysterectomy or bilateral oophorectomy, or are not naturally postmenopausal  $\geq 24$  consecutive months) must have negative urine or blood pregnancy test prior to enrollment and use adequate birth control methods (abstinence, oral contraceptives, barrier method with spermicide, or surgical sterilization) during study participation. Males must agree to use a latex condom during any sexual contact with females of child-bearing potential while participating in the study and for 12 weeks following the last dose of dalantercept, even if he has undergone a successful vasectomy. Patients must be counseled concerning measures to be used to prevent pregnancy and potential toxicities prior to the first dose of dalantercept.
10. Ability to adhere to the study visit schedule, and to understand and comply with protocol requirements.
11. Signed written informed consent.

**Exclusion Criteria:**

1. Clinically significant pulmonary, endocrine, neurologic, hematologic, gastrointestinal (GI), autoimmune, or genitourinary disease unrelated to RCC that in the judgment of the investigator should preclude treatment with dalantercept or axitinib.
2. Clinically significant cardiovascular risk including:
  - Ejection fraction (EF)  $\leq 50\%$  by echocardiogram (ECHO). Multi-gated acquisition scan (MUGA) should be obtained to estimate EF if quality of ECHO is not good.
  - Presence of grade 2 pericardial effusion on baseline ECHO.

- Significant history of congestive heart failure (CHF) defined as New York Heart Association (NYHA) class II-IV ([Appendix 3](#)).
  - Hospitalization for CHF (any NYHA class) within 6 months of study day 1.
  - Active coronary artery disease [e.g., myocardial infarction (MI), uncontrolled angina], peripheral vascular disease, cerebrovascular disease [e.g., transient ischemic attack (TIA), stroke], bypass surgery, angioplasty, or vascular stenting within 12 months prior to study day 1. Worsening symptoms attributable to cardiac or vascular disease and new findings on cardiac evaluation (e.g., clinical, stress test, etc.) within 3 months prior to study day 1.
  - Deep vein thrombosis (DVT) including tumor thrombus within 6 months of study day 1.
  - Significant arrhythmia or electrophysiologic disease including placement of implantable cardioverter defibrillator (ICD), atrial fibrillation with uncontrolled rate or prolonged QTc interval  $> 450$  ms for men and  $> 470$  ms for women.
  - Patients receiving cardiac medications should be on stable doses for at least 1 week prior to study day 1.
  - Uncontrolled hypertension defined as systolic blood pressure (BP)  $\geq 150$  mm Hg or diastolic BP  $\geq 95$  mm Hg. Patients with a history of hypertension must be well-controlled (BP  $< 150/95$ ) upon study entry using a stable regimen of anti-hypertensive therapy.
3. Known CNS metastases or leptomeningeal disease:
- For Part 1, patients with CNS metastases treated with whole brain radiotherapy, gamma knife, and/or surgery who are considered stable by CNS imaging and are not being treated with corticosteroids 6 weeks prior to study day 1 may be enrolled.
  - For Part 2, patients with CNS metastases treated with stereotactic radio-surgery (SRS) and/or surgery who are considered stable by CNS imaging for at least 2 monthss prior to enrollment and are not being treated with corticosteroids to manage their CNS disease within 4 weeks prior to study day 1 may be enrolled.
4. Active GI bleeding, unrelated to cancer, as evidenced by hematemesis, hematochezia, or melena within 3 months prior to study day 1 without evidence of resolution documented by endoscopy or colonoscopy.
5. Any active malignancy, other than RCC, for which chemotherapy or other anti-cancer therapy is indicated. Patients with adequately treated non-melanoma skin cancer or in situ cancer are permitted. Patients with other cancers from which they have been disease-free for at least 3 years will be permitted.
6. Any lesion invading or having encasement  $\geq 180$  degrees around the wall of a major blood vessel as assessed by computed tomography (CT) scan and/or magnetic resonance imaging (MRI).
7. Radiotherapy within 2 weeks prior to study day 1.
8. Lack of recovery from toxic effects of previous treatment for RCC to  $\leq$  grade 1 with the

exception of alopecia, unless stabilized under adequate medical control.

9. Systemic steroids or immunosuppressive agents within 1 week of study day 1 (with the exception of corticosteroids for CNS disease, see [Exclusion #3](#) or physiologic doses of corticosteroids) or biologic anti-inflammatory immune modulating agents (e.g. infliximab) within 4 weeks of study day 1.
10. Patients undergoing renal dialysis.
11. Major surgery within 4 weeks prior to study day 1 (patients must have recovered completely from any previous surgery prior to study day 1).
12. Any active infection requiring antibiotic therapy within 1 week of study day 1.
13. Anti-coagulation therapy. Aspirin, other anti-platelet agents, and low molecular weight heparin are permitted unless the investigator deems the patient is at a significant risk for bleeding.
14. Current use or anticipated inability to avoid strong CYP3A4/5 inhibitors or inducers (please refer to the Inlyta® [axitinib] prescribing information) during participation in the study.
15. Peripheral edema requiring medical intervention within 2 weeks prior to study day 1.
16. BMI < 16 kg/m^2.
17. Clinically significant active pulmonary risk including pulmonary hypertension and pulmonary edema within 12 months of study day 1 or pulmonary embolism within 6 months of study day 1.
18. Bleeding diathesis including clinically significant platelet disorders or active hemoptysis (defined as bright red blood of  $\geq 1/2$  teaspoon [2.5 mL] in any 24 hour period) within 6 months prior to study day 1. For clinically significant epistaxis within 4 weeks prior to study day 1, no risk of further bleeding must be clearly documented.
19. Known history of hereditary hemorrhagic telangiectasia (HHT).
20. Known active hepatitis B virus (HBV) or hepatitis C virus (HCV) infections or positive human immunodeficiency virus (HIV) antibody results. Patients with sustained virologic response to HCV treatment or immunity to HBV from prior infection without cirrhosis may be included.
21. History of severe (defined as  $\geq$  grade 3, using the National Cancer Institute Common Toxicity Criteria for Adverse Events, version 4.0 [NCI-CTCAE] v4 current active minor version) allergic or anaphylactic reaction or hypersensitivity to recombinant proteins or excipients (10 mM Tris buffered saline) in the investigational agent.
22. Any prior treatment with dalantercept or any other agent targeting ALK1 pathway.
23. Any prior treatment with axitinib.
24. A morbidity (per the Inlyta® [axitinib] prescribing information) that would require starting a patient at a reduced dose of axitinib.
25. Treatment with another investigational drug (with the exception of anticancer immune therapy) or device, or approved therapy for investigational use, within 5 times the half-life of the drug or within 3 weeks prior to study day 1 if the half-life is not known.

26. Pregnant or lactating female patients.

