#### **7.4. Potential Risks of Human Use of Dalantercept**

Dalantercept is designed to bind to the protein ligands BMP9 and BMP10 to inhibit their interaction with the ALK1 receptor, thus blocking a cell signaling process involved in angiogenesis. Effects on other organ systems, including erythropoiesis, may also be related to ALK1 or BMP9/10 inhibition.

The most frequently observed AEs ( $\geq 10\%$  patients) in the dalantercept monotherapy clinical trials (A041-01, A041-03) as of September 10, 2013 were fatigue, peripheral edema, headache, anemia, dyspnea, nausea, constipation, vomiting, anorexia, pyrexia, abdominal pain, cough, dehydration, epistaxis, hyponatremia, telangiectasia, diarrhea, hypotension, insomnia, arthralgia, back pain, dizziness and pleural effusion.

As of September 10, 2013, the most frequently observed AEs ( $> 20\%$  of patients,  $n=10$ ) in this study with the combination of dalantercept plus axitinib, regardless of causality, have included dysphonia, fatigue, diarrhea, arthralgia, constipation, hypertension, blood alkaline phosphatase increased, blood creatinine increased, chills, cough, dizziness, headache, hyperkalemia, muscle spasms, nausea, thrombocytopenia and vomiting.

On the basis of toxicology data in rats and monkeys and the preliminary clinical data, patients with significant cardiac risk will be excluded from participating in dalantercept studies and eligible patients will undergo comprehensive cardiac assessments which include, but are not limited to ECHO, electrocardiogram (ECG), laboratory testing, vital signs, and clinical evaluation.

Other potential risks associated with inhibition of ALK1 signaling may be inferred from the phenotypic findings in humans deficient in ALK1 expression. In humans, inactivating mutations in one copy of the ALK1 gene leads to a form of hereditary hemorrhagic telangiectasia (HHT). Hereditary hemorrhagic telangiectasia is characterized by recurrent epistaxis and telangiectasia, and in more severe cases, arteriovenous malformations (AVMs). To date, telangiectasia and epistaxis have been reported in the Phase 1 clinical study (A041-01); however, AVMs have not been reported in that study, nor were AVMs observed in toxicology studies with dalantercept. As a precaution, patients with a significant bleeding risk will be excluded from participating in dalantercept studies.

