[Table 3](#) describes the management of related AEs and required dose modifications for dalantercept/placebo. For any AE, including AEs not specifically mentioned in the table below, the investigator may decide to delay dosing or modify the dose level of dalantercept/placebo based on their clinical judgment. If possible, these decisions should be discussed with the medical monitor prior to implementation. If more than 1 AE occurs that would require a dose modification, upon resolution of all AEs to baseline or grade 1, dalantercept/placebo should be reduced two dose levels, or the patient should discontinue treatment. If a patient has a repeating AE or an AE of similar nature that would require a dose modification, the patient should be dose reduced to the next dose level or the patient should discontinue treatment depending upon the nature of the AE and the patient status. The rules for management of AEs described in [Table 3](#) are applicable to all scheduled visits as well as any unscheduled visits. Refer to [Table 4](#) and [Table 5](#), Dose Level Modifications, for dose level reductions.

Adverse events must resolve as outlined in [Table 3](#) prior to further dosing. For individual patients judged by the investigator to be at an unacceptable risk, despite not meeting the protocol-defined conditions for a dose modification, the investigator should consult with the medical monitor to decide whether to continue dosing at the same dose level, reduce the dose level, or discontinue the patient's treatment with dalantercept/placebo.

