1. $\geq$ Grade 2 bleeding event with the exception of grade 2 epistaxis	
 
● Discontinue further dalantercept/placebo treatment.
 
	
2. Any other event $\geq$ Grade 3 [e.g., hyponatremia (< 130 mmol/L)] with the exception of $\geq$ Grade 3 amylase and/or lipase in the absence of clinical symptoms.	
 
● Hold dalantercept/placebo treatment until resolution of AE(s).
 
● Work up as appropriate (e.g., serum and urine osmolality, serum and urine sodium, etc.).
 
	
 
2. Upon resolution of AE(s) to grade 1 or baseline, dalantercept/placebo should be reduced one dose level.
 

a Investigators can administer fluid management therapy as described in [Section 10.6.3](#) (Fluid Management Therapy).

b Note that treatment with diuretics is expected for some patients during this study and should not be used to determine grading of hypertension.

Patients are allowed up to 3 dose modifications (Table 3) due to AEs (e.g., from 0.9 mg/kg to 0.68 mg/kg, from 0.68 mg/kg to 0.51 mg/kg, and from 0.51 mg/kg to 0.38 mg/kg).

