#### **Events Not to Be Considered as Adverse Events**

Pre-existing medical conditions/signs/symptoms present before the screening period that do not worsen in severity or frequency during the study are defined as baseline medical conditions, and are not to be considered AEs.

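### No listed criterion expressly bars active GI bleeding from an RCC lesion, so the criteria only partly deliver the bleeding-risk exclusion intended in protocol section 7.4

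*Combined protocol and SAP*

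**What the plan says.** Exclusion 4 reads the same in the protocol synopsis and in section 9.3.2: "Active GI bleeding, unrelated to cancer, as evidenced by hematemesis, hematochezia, or melena within 3 months prior to study day 1". It applies only where resolution has not been shown by endoscopy or colonoscopy.

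Section 7.4 links ALK1 inhibition to features of hereditary hemorrhagic telangiectasia and then says: "As a precaution, patients with a significant bleeding risk will be excluded from participating in dalantercept studies". It sets no threshold for a significant risk and makes no exception for bleeding from tumor.

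Three other exclusions come closest to the same ground:

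- Exclusion 18: "Bleeding diathesis including clinically significant platelet disorders or active hemoptysis", with a 6-month look-back and a volume threshold for the hemoptysis. It mentions no cause. It also covers recent epistaxis.
- Exclusion 1, whose list of organ-system disease includes GI disease and ends: "genitourinary disease unrelated to RCC that in the judgment of the investigator should preclude treatment with dalantercept or axitinib".
- Exclusion 13, on anticoagulation, where aspirin, other anti-platelet agents and "low molecular weight heparin are permitted unless the investigator deems the patient is at a significant risk for bleeding".

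On treatment, Table 3 in section 10.6.1 stops dalantercept/placebo at or above a "Grade 2 bleeding event with the exception of grade 2 epistaxis". The text introducing the table says that it "describes the management of related AEs and required dose modifications for dalantercept/placebo".

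**The concern.** Bleeding is a recognized hazard of this regimen. Section 7.3 reports more epistaxis and telangiectasia at higher dalantercept doses. Related bleeding of grade 2 or higher is a dose-limiting toxicity (section 10.7). Section 10.6.2 names hemorrhage among the events that may require axitinib to be interrupted or stopped, and both arms receive axitinib.

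Against that background the cancer qualifier works in an odd direction. A patient with a benign GI bleed in the past 3 months must have endoscopic or colonoscopic proof of resolution. A patient with ongoing melena from an RCC lesion needs none. Active hemoptysis that meets exclusion 18 also keeps a patient out even when a lung metastasis is the source. At stake is avoidable bleeding risk for an individual patient at entry, not the validity of the primary comparison.

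**Working it through.** The only arithmetic is the share of one patient. The rest is a comparison of texts.

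**Step 1. Is the qualifier operative text?** Yes. It stands in identical form in the synopsis and in section 9.3.2, so it is not a slip in the summary.

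**Step 2. Which cancer does it concern?** In practice RCC, because exclusion 5 removes most other active malignancies.

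**Step 3. Does another listed criterion catch the patient?** The test case is active, unresolved GI bleeding from an RCC lesion. All 11 inclusion and 26 exclusion criteria were read against it. The nearest are:

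| Criterion | Reach | Bars the test case? |
|---|---|---|
| Exclusion 1 | Investigator judgment, but only on disease not due to RCC | No |
| Exclusion 6 | Invasion or encasement of a major blood vessel | Only if that is also present |
| Exclusion 8 | Unresolved toxicity of earlier RCC treatment | Only if the bleed is attributed to that treatment |
| Exclusion 13 | Bleeding risk as a limit on permitted anti-platelet agents and heparin | Not as a stand-alone rule |
| Exclusion 18 | Diathesis, platelet disorders, hemoptysis, epistaxis | Not expressly; a local tumor bleed is not ordinarily a diathesis |
| Exclusion 24 | Conditions needing a reduced axitinib starting dose | Not expressly |
| Inclusions 6, 7, 8 | ECOG 0 or 1; life expectancy of at least 12 weeks; hemoglobin of at least 9 g/dL | Filter some patients; none names bleeding |

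**Step 4. Does section 7.4 bar the patient directly?** No. It is background text stating an intent. Eligibility is decided by the listed criteria.

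**Step 5. What protects the patient after entry?**

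- Section 14.1 treats as baseline, and not as adverse events, "Pre-existing medical conditions/signs/symptoms present before the screening period that do not worsen in severity or frequency during the study". A stable bleed that predates screening falls here. One that starts during screening, or worsens, does not.
- If the bleed worsens, Table 3 applies to related events. Take related to mean possibly or probably, as in the definition of dose-limiting toxicity. Under section 14.4, possibly needs only a plausible cause and plausible timing, and given the mechanism an investigator could well choose it. The stop rule then applies from grade 2. If the known tumor is judged the cause and a drug relationship improbable, it does not.
- Section 10.6.1 allows dosing to be delayed or modified for any adverse event. It also directs the investigator to the medical monitor for a patient at unacceptable risk who meets no listed condition. Section 10.6.2 allows axitinib to be held or stopped.
- The DMC first reviews safety after 25 patients are randomized, then about every 6 months (section 10.7).

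Each of these acts after the first dose.

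**Step 6. Size.** Part 2 plans 130 patients, 65 per arm. One affected patient is 1/130 = 0.77% of the sample, or 1/65 = 1.54% of an arm. These are the shares of any single patient. They are not estimates of how often the case occurs, and the documents give nothing from which to estimate that.

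**The case against.** The strongest reply is that this is a deliberate choice with adequate cover. The qualifier appears in both places and parallels the wording of exclusion 1. The missing rationale does not prove an error. Section 7.4 speaks of dalantercept studies in general, and the protocol acts on it through exclusions 4, 6, 13, 18 and 19. Exclusion 18 concerns another site, with its own look-back and volume threshold, so different rules for lung and gut need not agree. Much of this stands. A reader might infer that the protocol contradicts itself, but the documents show only that a broad intent is incompletely carried into the criteria.

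A reader might also infer that the stop rule would miss such a patient. That goes too far. As set out above, a worsening bleed can be rated possibly related, and investigators keep wide discretion. What remains is that these protections follow exposure and depend on judgment, whereas an entry criterion does not.

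The axitinib prescribing information is a further reservation. Sections 7.5 and 10.6.2 send investigators to its warnings, and section 10.5 has axitinib given in line with it. It may already restrict such patients. It is not among the documents, and neither is the Investigator's Brochure, so this can be neither assumed nor ruled out.

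Finally, excluding a patient does not necessarily spare them axitinib, which section 7.1 lists among the approved therapies. The risk that is clearly specific to the trial is the addition of dalantercept, in one arm.

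**Conclusion.** The point holds as a narrow entry-safety gap of low priority. Followed as written, the criteria can admit a patient with active GI bleeding from an RCC lesion, although section 7.4 intends to keep out patients at significant bleeding risk. This rests on two readings: that such a patient carries a significant bleeding risk, which section 7.4 leaves undefined, and that a local tumor bleed is not a bleeding diathesis under exclusion 18.

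Frequency is unknown and probably low. Section 7.1 does not list the GI tract among the most common metastatic sites, and the hemoglobin, performance-status and life-expectancy criteria remove some candidates. The documents give no reason to infer a material effect on PFS, power or sample size, and none is claimed.

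**What to change.** In exclusion 4, delete the three-word qualifier between the first and second commas, in the synopsis and in section 9.3.2. Keep the allowance for resolution documented by endoscopy or colonoscopy, so that a patient whose tumor-related bleed has been treated and shown to have resolved can still enter.

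The change can go into the next amendment. It would add a few screen failures at most, each 0.8% of the 130 planned for Part 2. Some patients with a tumor-related GI bleed in the prior 3 months would need documented resolution, which may mean an added invasive procedure or loss of access to the trial. This is the same proof already asked of patients with non-cancer bleeding, and section 7.1 lists several approved therapies outside the trial. If the sponsor intended the qualifier, the alternative is to keep it and state the reason, including why exclusion 18 treats hemoptysis differently.
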